FinSote surveys 2018 and 2020 are based on a stratified random sample design that represents the Finnish population. However, non-participation in the survey could potentially introduce nonresponse bias if participants are systematically different from non-participants. For this purpose, we will take into account the complex survey design in all analyses and use the inverse probability weights (IPW) created by the Finnish Institute for Health and Welfare using a model with register-based data for the whole sample on age, sex, marital status, educational level, mother tongue and place of residence. The IPW method allows correcting for survey non-participation and the weighting factor of each participant is a combination of the inverse of the participation probability and the sampling probability. Hence, the set of weighted coefficients represents the Finnish population.³⁴

Information bias

The risk of information bias from measurement error of the exposure and confounders is inherent to most population health surveys. However, our data is almost entirely collected before assessment of the outcome, reducing the possibility that the exposure is affected by the occurrence of the outcome (i.e. that COVID-19 vaccination affects tobacco use). COVID-19 vaccination in Finland started on December 27, 2020, with a focus on health and residential care workers. The number of doses available in the first months was limited, so it is unlikely that participants from FinSote 2020 received the vaccination before the data collection. As sensitivity analyses, we will carry out the same analyses but excluding participants who have received a vaccination dose prior to February 8, 2021, when the data collection of FinSote 2020 ended. In addition, smoking status was collected relatively close to the COVID-19 vaccination, reducing (although not excluding it completely) the risk of exposure misclassification.

The COVID-19 vaccination has been implemented nationally by public providers, meaning that all COVID-19 vaccines provided have been registered in the Finnish National Vaccination Register. We estimate the risk of loss to follow-up and information bias of the outcome to be close to zero.

Study size

The sample size was determined by the available data from FinSote surveys 2018 and 2020. We consider it not necessary to provide a sample size calculation.

Quantitative variables

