We described the categorisation of exposures and confounders above. We will model age as a continuous variable and tested non-linearity by comparing the linear model with penalised smoothing splines using a likelihood ratio test.³⁵ The variable years of education will be modelled as categorical to be able to account for secular changes in years of education during the study years. In other words, educational attainment increases over time and it is therefore more appropriate to calculate the educational attainment within each survey wave.

Statistical methods

We will use Poisson regression with robust standard errors to estimate the relative risk of confirmed COVID-19 cases. We will fit the following Poisson model:

$$(1) \quad \log \mu_i = \beta_0 + \beta_1 S_i + \beta_x X_i^* + \rho_1 R_a$$

where i denotes the individual, β_0 is the intercept; β_1 is the coefficient of interest for exposure to tobacco S ; a vector of covariates X^* (i.e., sex, age, marital status, years of education, mother tongue and participation in social activities); and fixed effects $\rho_1 R_a$ for wellbeing area a . We will report the exponentiated coefficient as the relative risk estimate for unadjusted and adjusted models with their corresponding 95% confidence intervals.

We will examine non-linearity between age and the outcome by comparing the linear model with penalised smoothing splines³⁵ using a likelihood ratio test with the Wald method.³⁶ We will use the model with splines if it performs better than the linear model, using a p-value of 0.05 as the threshold for this decision.

We will examine potential effect modification by reporting stratified analyses by age, sex and educational level. If there are noticeable differences, we will test for multiplicative interactions between tobacco use and sex, age and educational level by including an interaction term in equation 1. We will introduce the interaction terms one by one for each of the examined interactions. We will use a likelihood ratio test to compare the model with and without the interaction. A p-value lower than 0.05 in the likelihood ratio test will be used as an indication of the presence of an interaction. If there is evidence of an statistically significant interaction, we will include the interaction term in the final model.

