Our primary method to handle missing data will be multiple imputation, given that a missing at random assumption is the most likely in our data. We will examine patterns of missing data and use multiple imputation using chained equations (MICE). This procedure will be combined with the survey design tools to take the complex sampling design into account.

In sensitivity analyses, we will report estimates using complete case analyses (i.e. taking only the complex sampling design into account). We will also report the same estimates as the main analyses, but restricting the follow-up time to when vaccination coverage reached 60% and 80%. This will allow us to understand whether these associations changed over time and also provide estimates that might be comparable to countries with lower vaccination coverage, thus increasing the external validity of our estimates.

We will analyse the data using R version 4.1.1 and include the statistical code as a Supplementary Appendix.

References

- 2 Davies, N. G. *et al.* Estimated transmissibility and impact of SARS-CoV-2 lineage B.1.1.7 in England. *Science* **372**, eabg3055, doi:doi:10.1126/science.abg3055 (2021).
- 3 Campbell, F. *et al.* Increased transmissibility and global spread of SARS-CoV-2 variants of concern as at June 2021. *Euro Surveill* **26**, doi:10.2807/1560-7917.Es.2021.26.24.2100509 (2021).
- 4 Suthar, A. B. *et al.* Public health impact of covid-19 vaccines in the US: observational study. *BMJ* **377**, e069317, doi:10.1136/bmj-2021-069317 (2022).
- 5 Krause, P. R. *et al.* SARS-CoV-2 Variants and Vaccines. *New England Journal of Medicine* **385**, 179-186, doi:10.1056/NEJMsr2105280 (2021).
- 7 Kuodi, P. *et al.* Association between vaccination status and reported incidence of post-acute COVID-19 symptoms in Israel: a cross-sectional study of patients tested between March 2020 and November 2021. *medRxiv*, 2022.2001.2005.22268800, doi:10.1101/2022.01.05.22268800 (2022).

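### The likelihood ratio test that decides interactions has no fixed 5% level in a weighted Poisson model for yes/no outcomes, so it can miss real interactions or declare false ones

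*Combined protocol and SAP*

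**What the plan says.** All quotes are from the combined protocol and SAP.

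- Model (Statistical methods): "We will use Poisson regression with robust standard errors". The sentence goes on to name confirmed COVID-19 cases as the outcome. I read the model as meant for the vaccination outcomes, which are yes/no.
- Interactions (Statistical methods): stratified results come first. Then "If there are noticeable differences, we will test for multiplicative interactions", one interaction at a time, by comparing nested models. The rule is "A p-value lower than 0.05 in the likelihood ratio test will be used as an indication of the presence of an interaction", and if it is met, "we will include the interaction term in the final model".
- Age (Statistical methods): the choice between a linear term and a spline is made "using a likelihood ratio test with the Wald method".
- Survey design (Bias, Selection bias): "we will take into account the complex survey design in all analyses", with weights that combine the inverse participation probability and the sampling probability. The scale of the weights is not given.
- Missing data (Statistical methods): chained-equation multiple imputation is primary, and "This procedure will be combined with the survey design tools to take the complex sampling design into account". No rule is given for pooling the interaction test over imputations.

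**The concern.** The Poisson likelihood takes the variance of the outcome to be p. For a yes/no outcome it is p(1−p). Robust standard errors repair the variance of the coefficients, and so the confidence intervals, but leave the log-likelihood as it was. A likelihood ratio statistic is therefore not corrected by them.

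The weights add a second problem. Multiplying all weights by a constant leaves the estimates and their robust variance unchanged but multiplies the log-likelihood, and so the test statistic, by that constant. An ordinary weighted likelihood ratio test at 0.05 then has an error rate set by uptake, by the spread of the weights and by their average. None of these is controlled by the threshold.

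At stake is a planned effect-modification analysis and the form of the final model. Depending on how the weights are scaled, a real interaction may be left out or a false one put in.

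**Working it through.** The plan states no interaction effect, power or error rate, so there is no figure of its own to reproduce.

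**Inputs from the document.** N = 14,736 + 28,199 = 42,935 (Setting and participants). National two-dose uptake is 87.6% and booster uptake 65.1% (background), used as proxies. The 2020 survey has 61,600 sampled and 28,199 in the analysis.

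**Assumed.** Exposed share 10–15%; sexes 50:50; base risk 0.885; relative risk (RR) 0.95; design effect (deff) 2 from unequal weights; mean weights as listed.

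**Scale of the statistic.** Over the four exposure-by-sex cells with sizes n and risks p, the true variance of the log ratio of RRs, before the design effect, is Σ(1−p)/(np). The Poisson model takes it as Σ1/(np). Let k be their ratio. Under no interaction the ordinary statistic is approximately k × deff × (mean weight) × chi-square on 1 df.

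With p = 0.885 and 0.885 × 0.95 = 0.841:
- 10% exposed: k = 0.0001899 / 0.001225 = 0.155
- 15% exposed: k = 0.0001319 / 0.0008626 = 0.153

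**Size**, as P(chi-square on 1 df > 3.841 / (k × deff × mean weight)), at deff 2 and before any screen:

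| Mean weight | Multiplier | Size, formula | Size, simulation (15% exposed) |
|---|---|---|---|
| 1 | 0.31 | 0.04% | about 0.05% |
| 2.18 (= 61,600/28,199, inverse participation only) | 0.67–0.68 | 1.6–1.7% | 1.4–2% |
| 4.37 (further factor of 2, assumed) | 1.34–1.35 | 9.0–9.2% | 9–10% |
| 100 (assumed) | 30.6–31.0 | 72% | 73–74% |

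The test has its nominal size only where the multiplier is 1, that is at a mean weight of 1/(2 × 0.155) = 3.2 to 1/(2 × 0.153) = 3.3. A robust Wald test in weighted simulations at design effects of 1.5 to 3 rejected in 4.7–5.2% of null runs.

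**Power** at a ratio of RRs of 0.95, deff 2, mean weight 1. The effect is |log 0.95| = 0.0513. For 10% and 15% exposed, the Poisson standard errors are 0.0354 and 0.0297, and the robust ones 0.0209 and 0.0174.
- Likelihood ratio: Φ((0.0513 − 1.96 × 0.0354)/0.0209) = 19%; Φ((0.0513 − 1.96 × 0.0297)/0.0174) = 35%.
- Robust Wald: Φ(0.0513/0.0209 − 1.96) = 69%; Φ(0.0513/0.0174 − 1.96) = 84%.
- Simulation gave 20% and 35–36%, against 70% and 84–85%.
- At a ratio of 0.90 the likelihood ratio test has 94–99% power.

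**Planned four-level smoking variable by sex** (3 df, deff 2, mean weight 1; daily smokers 10–13%, only they differ by sex, all assumed). Likelihood ratio against robust Wald: 2–4% against 49–64% at 0.95, and 68–83% against 99–100% at 0.90.

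**Other outcomes**, mean weight 1. Booster (1 − 0.651 = 0.349): size 0.1%, 1.9% and 5.5% at deff 1, 2 and 3. A delay outcome at an assumed 5% prevalence (1 − 0.05 = 0.95): 4.4% at deff 1 and about 15% at deff 2.

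**The screen.** It can only remove rejections, so it cannot restore power, but it could remove false positives. At deff 2 the null standard error is √(2 × 0.0001319) = 0.0162 (15% exposed) or √(2 × 0.0001899) = 0.0195 (10%). An assumed screen at a 3% observed difference (|log 0.97| = 0.0305) would then let through about 6% or 12% of null cases (z = 1.88 or 1.56). The plan sets no threshold, so this protection cannot be counted on.

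**The case against.** The strongest reply is that the plan already implies a design-based test. The Selection bias section applies the survey design throughout, the missing-data paragraph brings in survey tools, the age comparison mentions a Wald method, and the code is to be published. If a design-based test is what will be run, its level is near 5% and the change only records the intention. This stands as a reason for moderation. It does not settle the matter: the general promise names no test, the specific instruction names a likelihood ratio test, and the age wording names two tests at once.

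A reader might infer something stronger: that the plan will systematically miss interactions in two-dose uptake, at a false-positive rate below one in a million. That rate is what an unweighted fit would give (multiplier 0.153–0.155). The documents do not support it, because they apply weights in every analysis and do not say that these are rescaled to average 1. On the weights as described, the error can go either way.

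Three further points stand. The size and power gaps rest on assumed exposure shares, effects and design effects, and all were computed for sex, none for age or education. The yes/no exposure is a simplification, since smoking has four levels and snus three. And the proposed test is no cure for low power: in the four-level case at a ratio of 0.95 it would still miss 36–51% of such interactions.

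**Conclusion.** The point holds as a fault of level, not of direction. Taken literally, the stated test is corrected neither for the yes/no outcome nor for the weights. With a design effect of 2 and a yes/no exposure by sex, its size for two-dose uptake runs from under 0.1% (mean weight 1) through about 10% (mean near 4) to about 70% or more (mean 100), before the undefined screen. In the first case, power at a ratio of RRs of 0.95 is 19–36% against 69–85%.

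That robust standard errors leave the statistic unchanged, and that it moves with the weight scale, is certain. The sizes depend on the assumptions listed, and on an ordinary test being run at all. The consequence is limited to the interaction decision and the final model. Stratified estimates by age, sex and education are reported regardless, and the main RRs and their robust intervals do not change. It should be corrected, but it does not threaten the primary estimate.

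**What to change.** In Statistical methods, replace the likelihood ratio test for interactions with a design-based Wald F test of all terms of the interaction on the robust survey covariance, or a Rao-Scott-adjusted likelihood ratio test. State that it is pooled over the imputations by Rubin-type rules. Name the same type of test for the choice between a linear and a spline term for age, in place of the present wording that names two tests.

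The cost is a few sentences of protocol text and a different test call in the same analysis. No new data are needed.

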Participants in the FinSote 2020 Survey were adults aged 20 and over derived from the Digital and Population Data Services Registry, created in Jan 2020 after the merge between the Population Register of Statistics Finland and local register offices.²⁹ This sampling frame includes all residents in Finland. The survey was based on a stratified random sample of 22 regions (2000 adults aged 20-74, 800 adults aged 75+, total sample size 61600). Data collection started on September 14, 2020, and finished on February 8, 2021. Participants received a self-administered questionnaire in Finnish, Swedish, English or Russian, which could be returned on paper or filled in electronically. The analytical sample is 28199 participants, with a participation rate of 46%. In 2020, consent to linkage was included in the overall consent, and as a result, we were able to link all participants in the analytical sample.

We will link data from FinSote 2018 and 2020 surveys to the Finnish National Vaccination Register maintained by the Finnish Institute for Health and Welfare using a unique identifier assigned to all residents in Finland. The follow-up will be between December 27, 2020 (date of the first COVID-19 vaccination in the country) until May 31, 2022 or the latest available date.

Outcomes

Our primary outcome will be the vaccination uptake of at least two doses of a COVID-19 vaccine. We will examine four secondary outcomes:

- (i) vaccination uptake of at least one dose of a COVID-19 vaccine,
- (ii) vaccination uptake of the complete COVID-19 vaccination scheme (two doses and a booster dose),
- (iii) proportion of participants with more than 7 months between the first and second COVID-19 dose, and
- (iv) proportion of participants with more than 7 months between second dose and booster dose.

We will include any approved COVID-19 vaccination in Finland by the latest available date (i.e. April 29, 2022):³⁰ COVID-19 mRNA vaccines (Comirnaty and Spikevax), recombinant vaccines (Vaxzevria, COVID-19 vaccine Janssen, COVISHIELD, Nuvaxovid, COVOVAX), and inactivated vaccines (BIBP/Sinopharm, COVAXIN, Coronavac). Participants who have received the COVID-19 vaccine Janssen would be excluded from analyses on the second dose, as the vaccine only requires a single dose.

Exposures

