We will examine two forms of tobacco use: smoking and smokeless tobacco (snus) use. We will assess smoking status with the following question: Do you smoke currently (cigarettes, cigars or pipe)? (a) yes, daily, (b) occasionally, (c) not at all, (d) I have never smoked. We will create a categorical variable with the following categories: never smokers, former smokers, current occasional smokers and current daily smokers.

We will assess snus use with the following question: Do you currently use any of the following products? Snus (Swedish type moist stuff) (a) yes, daily, (b) occasionally, (c) not at all, (d) I have never used. We will create a categorical variable with the following categories: never users, former users, current users (daily and occasional combined). Data on smoking status is available for all participants, while data on snus use was available for participants aged 20-74 years old.

Potential confounders

We will adjust for several potential sociodemographic confounders: age, sex, marital status, educational tertile, and participation in social activities. All variables will be analysed at baseline. We will define marital status as those married or in a registered relationship or cohabiting versus those separated or divorced, widowed or single. We will calculate educational tertiles for each survey year using the years of education reported in the question “How many years altogether have you attended school or studied full time?”. We will analyse participants’ mother tongue using data from national registries and will categorise it into three categories: Finnish, Swedish and other. We will measure participation in social activities with a question about participation in the activities of any club, association, hobby group or religious or spiritual community. We will categorise participation into the following: no participation, occasional and active.

Potential mediators

We will take the incidence of COVID-19 infections into account (see below). We will obtain data on confirmed COVID-19 cases from the Finnish National Infectious Disease Register maintained by the Finnish Institute for Health and Welfare. Confirmed COVID-19 cases will be defined as those cases with a positive SARS-CoV-2 RT-PCR, either informed by a laboratory or by a physician as a record of an ICD-10 code U07.1 (which requires a positive SARS-CoV-2 RT-PCR). Reporting of COVID-19 positive cases was mandatory for laboratories and physicians throughout the study period.

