Effect modifiers

We will examine potential effect modification by reporting stratified results by age (as a categorical variable), sex and educational level.

Data sources and measurement

[figure not shown]
Data sources and measurements for all variables were described above. More details on the exact variables can be found in the Supplementary Appendix.

Bias

Confounding bias

We will reduce the risk of confounding by adjusting for potential confounders that causally precede the exposure and are associated with the outcome. We built a directed acyclic graph to guide the identification of potential confounders and mediators (Figure 1). Adjusting for mediators can result in an underestimation of the association and potentially introduce M-bias (a type of collider bias).^{31,32}

Figure 1. Directed acyclic graph of the causal association between tobacco use and COVID-19 vaccinations uptake

A special concern were participants who had a COVID-19 infection. Tobacco use is associated with COVID-19 infection and, in turn, having a COVID-19 infection can influence the willingness to vaccinate or delay COVID-19 vaccination. Current Finnish guidelines recommend to the general adult population, after having a COVID-19 infection, to: (i) wait at least two months before getting the first COVID-19 dose, (ii) wait at least four to six months after the COVID-19 infection or the first dose, whichever happens first. People with two doses will not be given a third dose if they have had COVID-19. Having a COVID-19 infection, according to our DAG, would act as a mediator. Excluding individuals who have had the infection (or adjusting for it) would result in estimating the direct effect between tobacco use and COVID-19 vaccination uptake and not the total effect. For this reason, our main analyses will report the outcomes without adjusting for having a COVID-19 infection. In sensitivity analyses, we will report estimates stratified by COVID-19 infection status and also we will use causal inference methods (e.g. marginal structural methods and G-formula) to account for this time-varying estimate. We expect, however, that this will not make a large difference, as the COVID-19 incidence prior to the start of the COVID-19 vaccinations was very low and continued to be low until the rise of the Omicron variant in mid-December 2021.³³ In practice, this means that a very small proportion of our sample will experience a COVID-19 infection during the study period.

Selection bias

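### Up to 30 interaction tests at an uncorrected 0.05, chosen by an undefined look at the same data, can each rewrite a final model

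*Combined protocol and SAP*

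**What the plan says.** The Effect modifiers section commits to "reporting stratified results by age (as a categorical variable), sex and educational level". The Statistical methods section then adds a conditional step: "If there are noticeable differences, we will test for multiplicative interactions between tobacco use and sex, age and educational level". Nothing says how large a difference has to be, on what scale, or who judges it. On order, the plan says "We will introduce the interaction terms one by one for each of the examined interactions". On the decision, it says "A p-value lower than 0.05 in the likelihood ratio test will be used as an indication of the presence of an interaction". On the consequence, it says "If there is evidence of an statistically significant interaction, we will include the interaction term in the final model".

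The scope follows from two other sections. Under Exposures: "We will examine two forms of tobacco use: smoking and smokeless tobacco (snus) use". Under Outcomes: "Our primary outcome will be the vaccination uptake of at least two doses of a COVID-19 vaccine", followed by "We will examine four secondary outcomes". The interaction step is not limited to the primary outcome or to one exposure. It is not labelled exploratory, and no multiplicity correction appears anywhere in the document.

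**The concern.** Each test is judged alone at 5%, but the rule is open to many tests. With no true effect modification, some final models may still carry an interaction, presented as tobacco effects that differ by age, sex or education.

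The screen does not protect against this. It looks at the same stratum differences that the test then measures, so it tends to pass the combinations that are about to give a small p-value. It also makes the number of tests run smaller than the number of comparisons inspected.

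The consequence goes beyond a subgroup remark. In equation 1 of the Statistical methods section, β1 is the tobacco effect that the study is meant to estimate. Once a tobacco-by-modifier term is added, β1 is the effect at the modifier's reference value only. A chance hit therefore changes the meaning of the headline relative risk, including the one for the primary outcome.

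**Working it through.** The plan states no overall false-positive rate, so there is no figure to reproduce. The calculation starts from its own counts.

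**Inputs from the document**
- Exposures: 2 (smoking in four categories, snus in three).
- Outcomes: 1 primary + 4 secondary = 5.
- Modifiers: 3 (age, sex, educational level).
- Threshold per test: 0.05.
- National coverage in the introduction: 89.7%, 87.6% and 65.1% for first, second and booster dose. These stand in for uptake in the cohort.

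**Assumptions not in the document**
- Degrees of freedom for sex, age and education: 3, 3, 6 for smoking and 2, 2, 4 for snus.
- Correlations involving the spacing outcomes, and the prevalence of the spacing outcomes.

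**Step 1: count.** 2 × 5 × 3 = 30 tests at most; 2 × 3 = 6 for the primary outcome; 3 for any one exposure-outcome model.

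**Step 2: independent tests, true size 5%, no effect modification.** P(at least one hit) = 1 − 0.95^m.
- m = 30: 1 − 0.95^30 = 0.785; expected number of hits 30 × 0.05 = 1.5.
- m = 6: 1 − 0.95^6 = 0.265.
- m = 3: 1 − 0.95^3 = 0.143.

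**Step 3: overlapping outcomes.** The three uptake outcomes are nested. For nested proportions a > b, the correlation is √[b(1 − a) / (a(1 − b))]. The coverage figures give 0.90 (first and second dose), 0.51 (second dose and booster) and 0.46 (first dose and booster). Null simulation of all 30 tests, 100,000 runs:

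| Correlation between outcomes | At least one hit in 30 |
|---|---|
| None | 78.6% |
| Uptake outcomes as coverage implies, spacing outcomes independent | 73% |
| All five outcomes equally correlated at 0.3 | 76% |
| All five at 0.5 | 72% |
| All five at 0.7 | 64% |
| All five at 0.9 | 49% |

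The six primary-outcome tests share one outcome, so correlation between outcomes does not affect their 26%.

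**Step 4: what a screen might do.** Suppose a combination is tested only if at least one of its contrasts exceeds a cut-off in standard errors (an assumed form, since the plan gives none). With independent outcomes, the 30-test figure is about 79% at a cut-off of 1, 78% at 1.5 and 77% at 1.96. At 1.5, only about 25% to 58% of null combinations are tested, but about 9% to 20% of those tested give p < 0.05. Such a screen removes tests but few false hits.

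**Step 5: if the test is an ordinary Poisson likelihood ratio.** For a binary outcome with prevalence p, the Poisson variance is too large, and the statistic is scaled by about 1 − p. The true size is then P(χ² > c / (1 − p)), where c is the nominal 5% critical value.
- Six primary-outcome tests at p = 0.876: chance of any hit below 1 in a million. If weighting inflated the statistic threefold (assumed), it would still be below 0.1%.
- All 18 uptake tests: about 0.05%.
- All 30 tests: about 40%, 22% and 5% if both spacing outcomes have prevalence 5%, 20% and 40% (assumed).

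**The case against.** A reader might infer that the rule will produce a false interaction about three times in four. The documents do not support that as a plain statement. It needs all 30 tests to be run, or a screen that removes few hits. It needs little correlation beyond the uptake outcomes, and a true 5% size for each test. A screen can only remove tests, so 79% is an upper value. Thirty is also the broadest reading, since the plan does not say outright that the step is repeated for every outcome and exposure.

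The test size is the most important of these conditions. The Statistical methods section names a likelihood ratio test on a Poisson model, and robust standard errors do not correct an ordinary likelihood ratio. On that reading the primary-outcome tests would almost never fire. Against this, the Selection bias section says that the survey design enters every analysis, which points to a design-based test with size near 5%. The plan does not settle which is meant, so the figures must be given conditionally.

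A reader might also infer that a false interaction could not be told from a real one because the screened-out comparisons stay hidden. That is too strong. Stratified results are promised whether or not the screen is passed, and the code will be published. What is not promised is a count of the tests run, or p-values for comparisons that did not look different.

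Finally, strict family-wise control of exploratory effect modification in an observational cohort is a matter of judgement, and the plan treats p < 0.05 only as an indication. That stands, and it is why Holm's method is optional below. It does not defend an undefined screen, or a rule under which a single p-value changes the final model.

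**Conclusion.** The point holds in conditional form. The plan allows up to 30 uncorrected interaction tests, selected by an undefined look at the same data, each able to change a final model. With no effect modification, all tests run and a true 5% size, the chance of at least one false interaction is up to about 79%. It is about 73% with the uptake overlap that national coverage implies, and 49% to 76% across the common correlations tried for all five outcomes. Under the same size condition it is about 26% for the primary outcome and 14% for any one final model. With an ordinary Poisson likelihood ratio the total falls to about 5% to 40%, nearly all of it from the spacing outcomes.

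The problem that does not depend on these figures is the change in the meaning of β1 after a hit. The interaction step is supportive, so this does not undermine the main analysis, but it should be corrected before the data are analysed.

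**What to change.** In the Statistical methods section:

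1. Remove the screen on visible differences between strata.
2. List six interaction tests in advance, on the primary outcome only: two exposures by three modifiers.
3. Name a design-based test for them, such as a survey Wald or Rao-Scott test, and say how it is combined across the imputed data sets.
4. Report all six p-values and the number of tests, and label them exploratory. Holm's method across the six is an option. Its first threshold would be 0.05 / 6 = 0.0083, at some loss of power for weak interactions.
5. Keep the main-effects model as the headline estimate, with any interaction shown alongside it.
6. For the four secondary outcomes, report stratum-specific relative risks with 95% confidence intervals as descriptive, and do not change the final model.

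The cost is wording only, with no new data. The downside is that a real interaction on a secondary outcome would be visible only through the stratified results.
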